19.3. Sample Size

The following summarizes the sample size required to achieve 80% power separately for pigmentation Group A and Group B for their respective primary efficacy endpoints.

From Kung, et al, 2018, Graph 1 indicates that for clearance of pigmentation, 0% experienced complete improvement (Grade 5: >95%), 53.8% experienced excellent (Grade 4: 75-94%) improvement, while 30.8% experienced good (Grade 3: 50-74%) improvement from baseline. With 30 evaluable subjects, there is 80% power to reject a 50% improvement rate in favor of a 75% improvement rate according to a two-sided exact binomial test with 5% Type I error. Statistical significance will be achieved if █% improvement is observed at 12 week follow-up / study exit visit.

From Fitzpatrick, et al, 1996, Table 2 indicates for peri-orbital and peri-oral wrinkles, the mean changes from baseline to study exit were 2.34 points and 2.25 points with standard deviations < 2 points. With 34 evaluable subjects, there is 80% power to detect a 1-point improvement from baseline according to a two-sided paired t-test with 5% Type I error. Statistical significance will be achieved if a █ mean improvement is observed from Baseline to 12 week follow-up / study exit with a 2-point standard deviation.

19.4. Effectiveness Analyses

The skin pigmentation score will be evaluated using a paired t-test separately for the peri-orbital, peri-oral, and combined outcomes from baseline to study exit. In addition, the percentage achieving a 1-point improvement will also be displayed with two-sided 95% confidence intervals to support regulatory submissions requiring 1-point improvement analyses.

Wrinkle score improvement will be evaluated using a two-sided exact binomial test.

The Subject Pain Scale and Subject Satisfaction Score will be evaluated by displaying the distributions with the range, mean, and two-sided 95% confidence intervals provided. Results will be displayed separately for Groups A and Group B.

The effectiveness analyses will be performed using a Per Protocol (PP) population which excludes subjects with major protocol deviations such as subjects withdrawn prior to final evaluation.

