19.2. Hypotheses

Null and alternative hypotheses are stratum specific. They assess the change from Baseline to Week 12/study exit.

Pigment effectiveness (5-point ordinal scale, 5 is best) will be evaluated according to the following null and alternative hypotheses for Group A:

- Null Hypothesis: Less than 50% experience good to excellent improvement in the Pigment Clearance Score (PCS)
- Alternative Hypothesis: At least 80% experience good to excellent improvement in PIS.

Fitzpatrick Wrinkle Score (9-point ordinal scale, 1 is best) will be evaluated separately for peri-orbital wrinkles and peri-oral wrinkles as well as the sum according to the following null and alternative hypotheses for Group B:

- Null Hypothesis: There is no mean improvement in the Fitzpatrick Wrinkle Score (FWS)
- Alternative Hypothesis: There is at least a 2-point mean improvement in FWS.

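### Section 19.4 reverses the primary tests named and powered in 19.3, and swapping them back still leaves pigment with two competing primary endpoints

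*Combined protocol and SAP*

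**What the plan says.** **Section 19.4 (analysis).** For pigment: "The skin pigmentation score will be evaluated using a paired t-test separately for the peri-orbital, peri-oral, and combined outcomes". The same paragraph adds that "the percentage achieving a 1-point improvement will also be displayed with two-sided 95% confidence intervals". For wrinkles: "Wrinkle score improvement will be evaluated using a two-sided exact binomial test", with no null proportion and no definition of improvement.

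**Section 19.3 (sample size).** For pigment, 30 evaluable subjects give 80% power to reject a 50% rate "in favor of a 75% improvement rate according to a two-sided exact binomial test". For wrinkles, with 34 evaluable subjects, "there is 80% power to detect a 1-point improvement from baseline according to a two-sided paired t-test". The section says that these calculations serve each group's primary efficacy endpoint.

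**Section 19.2 (hypotheses).** No test is named. The pigment hypothesis is a good-to-excellent proportion: a null below 50% and an alternative of at least 80%. The wrinkle hypothesis is a mean change in FWS: no improvement against at least 2 points. The regions belong to wrinkles, which "will be evaluated separately for peri-orbital wrinkles and peri-oral wrinkles as well as the sum".

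**Synopsis, 17.1 and 17.3 (endpoints).** The primaries are the mean PCS difference and the mean FWS difference from baseline to week 12. The share of subjects with PCS 3 or 4 is secondary, as is the share gaining at least 1 FWS point by agreement of two of three evaluators.

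**PCS scale.** Section 9.1 describes a scale from 0 (no improvement) to 4 (75-100%). Section 19.2 and Appendix A use five grades with 5 best; in Appendix A, 1 is 0-24% and 5 is at least 95%.

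**The concern.** A statistician who follows 19.4 to the letter would analyse neither group with the test on which its sample size rests. The wrinkle binomial test could not be run without inventing a null and a cut-off, and the declared wrinkle primary would have no test. The pigment t-test would be split by facial regions, although section 7 admits pigmented lesions on the scalp, neck, chest, back, arms, hands, legs and feet as well as the face.

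The wrinkle half can be put right by reading 19.4 against the other sections. The pigment half cannot. A test of a mean fits the endpoint declared in 17.1, and the binomial test fits the hypothesis and power in 19.2 and 19.3. Either could be defended as the primary analysis after the data are seen. Section 19.4 says that part of this analysis is meant to support regulatory submissions, so that freedom matters.

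**Working it through.** **1. Pigment size with 19.3's test.** Inputs from 19.3: n=30, null 0.50, alternative 0.75, two-sided 5%. Reject at the smallest r with 2 × P(X ≥ r | 30, 0.50) ≤ 0.05.
- r=20: 2 × 0.0494 = 0.0987, not significant.
- r=21: 2 × 0.0214 = 0.0428, significant. The threshold is 21/30 = 70.0%.
- Power = P(X ≥ 21 | 30, 0.75) = 80.3%.

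**2. Wrinkle size with 19.3's test.** Inputs from 19.3: n=34, mean change 1, SD 2, two-sided 5%. Non-centrality = (1/2) × √34 = 2.915 on 33 degrees of freedom.
- Power = 80.8%.
- n=33 gives 79.5%, so 34 is the smallest size that reaches 80%.

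Both stated sizes reproduce.

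**3. The tests as assigned in 19.4.** Neither has the inputs for a calculation. The pigment t-test has no planning mean, SD or reference value. The wrinkle binomial test has no null proportion or cut-off.

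**4. Side by side.**

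| | Synopsis, 17.1 (primary) | 19.2 | 19.3 | 19.4 |
|---|---|---|---|---|
| Pigment | mean PCS difference | proportion against 50% | exact binomial | paired t-test by facial region |
| Wrinkles | mean FWS difference | mean change, by region and sum | paired t-test | exact binomial |

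In the wrinkle row only 19.4 is out of line. In the pigment row the declared primary is a mean, and the tested and powered quantity is a proportion that 17.3 lists as secondary.

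**5. Can PCS be paired?** PCS grades improvement from baseline, and 8.1 grades baseline pigment on a different scale, the Pigment Severity Score. There is therefore no baseline PCS to subtract. A mean analysis would have to be a one-sample test against a reference value. On the 0-4 scale, 0 is a natural choice. On Appendix A, where grade 1 spans 0-24%, no reference value is stated.

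**6. Who is a responder?** On the 0-4 scale, grade 4 reaches 100%. Grades 3 and 4 then take in everyone with at least 50% clearance, if the lower limit of grade 3 is read from the gloss in 17.3. On Appendix A, grades 3 and 4 run from 50% to 94%, so by number they leave out grade 5, although the gloss (over 50% improvement) would include it.

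**7. Alternatives.** Section 19.2 states 80% and 2 points; 19.3 powers 75% and 1 point. At 19.2's values the same sizes give P(X ≥ 21 | 30, 0.80) = 93.9% for pigment. For wrinkles the non-centrality is (2/2) × √34 = 5.83, and power is over 99.9%. The mismatch does not undermine n, but the text should state one alternative per group.

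**The case against.** The strongest reply is that two paragraphs were transposed. The facial regions and the 1-point percentage plainly belong to wrinkles, and 19.1 calls for a SAP finalised before study initiation that could put the tests right. For wrinkles this largely stands: the intent can be recovered. For pigment it does not. A SAP cannot choose between two primaries that the protocol itself states without a protocol change.

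It can also be said that the binomial test was meant for the secondary 1-point FWS endpoint. Section 19.4 does not say so, still gives no null, and would then leave the primary mean FWS change untested.

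A third reply is that the pigment t-test agrees with the synopsis and 17.1, so the responder proportion need not be the primary. That is fair. The choice is the sponsor's, but a mean primary needs its own hypothesis, reference value and power.

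Some stronger readings go beyond the documents:
- A reader might infer that the wrinkle binomial test is badly underpowered at 34. With no null or cut-off stated, any power figure rests on invented inputs and also turns on whether change is treated as continuous or as whole points.
- A reader might infer that the sample sizes are wrong. They reproduce.
- A reader might infer that complete responders will be excluded. That follows only from reading grade numbers on Appendix A. The 0-4 scale and the gloss in 17.3 include them, and 19.3 cites 0% complete response in the source study.
- A reader might infer that three FWS outcomes leave the study short of power. Which outcome n=34 covers is not stated, and neither is a planning effect or SD for the sum. The documents support asking for the primary to be named, not a power loss of a given size.

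**Conclusion.** The point holds. Section 19.4 reverses the tests named and powered in 19.3 and does not match the hypotheses in 19.2. As written, it gives the wrinkle score a test that lacks a null and a cut-off, leaves the wrinkle primary without a test, and asks for a paired test of a score that has no baseline value. Separately, the pigment primary is a mean in the synopsis and 17.1 and a responder proportion in 19.2 and 19.3, on a scale that differs between sections.

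The size of the problem is that neither 19.4 test has a sample size behind it, while the powered tests deliver 80.3% (n=30) and 80.8% (n=34) under 19.3's own assumptions. No loss of power or inflation of error can be quantified from the documents, and none is claimed. Confidence in the contradiction is high, because it rests on the text and on the reproduced sizes. The text must be corrected before the analysis, since two defensible pigment primaries would otherwise remain open.

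**What to change.** In 19.4:
- Group A: two-sided exact binomial test of the proportion with at least 50% clearance, against 50%.
- Group B: paired t-test of FWS change, with the regional split and the 1-point responder percentage with its 95% confidence interval attached to FWS.

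In the same amendment:
- Make the pigment primary identical in the synopsis, 17.1, 17.3, 19.2 and 19.3. Either adopt the powered responder proportion and report mean PCS descriptively, or keep mean PCS and supply a one-sample hypothesis, a reference value and a power calculation; 19.4 must then follow that choice.
- Use one PCS scale in 9.1, 17.3, 19.2 and Appendix A. Define a responder as every grade with at least 50% clearance, including complete response, and match the evaluators' scoring form to it.
- Align the alternatives in 19.2 (80%; 2 points) with those powered in 19.3 (75%; 1 point).
- State which FWS outcome (peri-orbital, peri-oral or the sum) is the primary test that n=34 covers.
- Carry all of this into the SAP that 19.1 requires.

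The cost is a text amendment and, depending on the scale chosen, a revised scoring form. With the responder proportion as primary, n stays at 30 and 34. Keeping mean PCS requires a new power calculation for Group A.

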17.1. Primary Effectiveness Endpoints

Benign Pigmented Lesions

Mean difference from Baseline to final 12-Week follow-up visit in Pigment Clearance Score as determined by blinded evaluators from clinical photographs.

Wrinkles

Mean difference from Baseline to final 12-Week follow-up in Fitzpatrick Wrinkle Score as determined by blinded evaluators from clinical photographs.

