19.1. Statistical Plan Overview

The study will be conducted with two separate strata (pigment, wrinkles) which will be evaluated. Benign pigmented lesions including dyschromia (Group A) and wrinkles including fine lines (Group B) will be separately powered and analyzed for efficacy and safety while both groups will further be combined for safety analyses. All study sites will be eligible to enroll subjects into each stratum; no subject will be enrolled into both strata.

Subjects participating in the pigment treatment stratum will be evaluated using the Pigment Clearance Score (Appendix A) while subjects participating in the wrinkle treatment stratum will be evaluated using the Fitzpatrick Wrinkle Score (Appendix B). All study subjects will also be evaluated using the Subject Pain Scale (Appendix C), Subject Satisfaction Survey (Appendix D), the Local Skin Response (Appendix E), and will be evaluated for safety according to 21 CFR Part 812 as well as ICH guidelines (E3 and E6) and ISO 14385:2016 as applicable.

A statistical analysis plan (SAP) will be finalized prior to study initiation. The database will be constructed using Microsoft Office Excel (Microsoft, Redmond, WA). The database will be locked following a review of all protocol deviations to be classified as a major or minor deviation. Major and minor protocol deviations will be reviewed once all data undergo source document verification and prior to database lock. The independent biostatistician will determine major vs. minor protocol deviations.

Data analyses will be performed using SAS Version 9.3 or later (SAS Institute, Cary NC) and StatXact Version 10 or later (StatXact, Cambridge MA). All analyses will be performed in a GCP environment controlled by SOPs.

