19.5. Safety Analyses

Safety will be evaluated using the Local Skin Response (Appendix E) which will specifically assess the following nine pre-defined safety endpoints: erythema, edema, whitening, petechiae, pinpoint bleeding, purpura, crusting, blistering, burn, as well as other to be graded on a 5-point ordinal score.

Safety will be evaluated in the Intent to Treat (ITT) population which includes all treated subjects. Safety results will be displayed separately for Groups A and Group B. Analyses will include a summary of the incidence, severity, and relatedness of all reported local skin responses, adverse device effects, and unanticipated adverse device effects. In addition, the percentage with no adverse device effects will also be reported as well as the percentage according to worst overall degree; a similar evaluation will be performed for the worst degree for those at least related to the study treatment. The percent reporting each ordinal score per safety endpoint will be presented separately for each stratum and combined.

20. Histological Analysis

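### Effectiveness is planned only in a per-protocol set that drops withdrawn subjects; an all-treated analysis should stand beside it, because the Group A responder rate is overstated if withdrawn subjects respond less often

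*Combined protocol and SAP*

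**What the plan says.** Section 19.4 places the effectiveness analyses in a "Per Protocol (PP) population which excludes subjects with major protocol deviations such as subjects withdrawn prior to final evaluation". Section 19.5 defines the wider set and gives it one use: "Safety will be evaluated in the Intent to Treat (ITT) population which includes all treated subjects". Section 7 allows subjects who withdraw or are terminated to be replaced.

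For Group A, the null hypothesis in section 19.2 is "Less than 50% experience good to excellent improvement in the Pigment Clearance Score (PCS)". Section 19.3 sizes the matching test: "With 30 evaluable subjects, there is 80% power to reject a 50% improvement rate in favor of a 75% improvement rate", using a two-sided exact binomial test at 5%. Section 17.3 lists the responder percentage as a secondary endpoint.

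Other sections point to a mean instead. Section 17.1 defines the pigment primary endpoint as "Mean difference from Baseline to final 12-Week follow-up visit in Pigment Clearance Score as determined by blinded evaluators", and section 19.4 says "The skin pigmentation score will be evaluated using a paired t-test".

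Section 19.1 adds two relevant statements: "A statistical analysis plan (SAP) will be finalized prior to study initiation" and "The independent biostatistician will determine major vs. minor protocol deviations". The second step is placed before database lock. No separate SAP is among the documents. The supplied text gives no withdrawal rate, no rule for a missing 12-week score and no sensitivity analysis for effectiveness.

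**The concern.** The study has no control arm; each subject is compared with his or her own baseline. If subjects who leave early tend to be those who respond poorly, no comparison group suffers a similar loss to offset it. Replacement restores the number of evaluable subjects but not the subjects who were lost.

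Selective loss is plausible. Section 7 allows termination to protect a subject's health, and section 10.2 lists hyper- and hypopigmentation among the anticipated device effects, so a Group A subject could leave for a reason tied to the endpoint. Table 1 runs to about week 30, which gives a dissatisfied subject time to leave. At stake are the Group A responder rate and its test against 50%. The deviation review and the all-treated safety counts could show how many subjects were lost, but no planned analysis shows what that loss does to the responder rate.

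**Working it through.** **Inputs from the documents.** Group A: 30 evaluable subjects, null 50%, alternative 75%, two-sided exact binomial test at 5% (section 19.3). Group B: 34 evaluable subjects, 1-point change, SD 2, two-sided paired t-test at 5% (section 19.3). Enrolment: up to 160 in total, with no split by group (section 7).

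**Assumptions.** The share withdrawn, d, and the response rate among withdrawn subjects, q. The documents give neither, so ranges are shown.

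**1. The plan's own figure.** The Group A threshold is redacted, so it is derived. With n = 30 and a null of 0.5, 21 is the smallest count that is significant: P(X ≥ 21) = 0.0214, two-sided p = 0.043. For 20 the two-sided p is 0.099. Power at 75% is P(X ≥ 21 | 0.75) = 0.803, which reproduces the stated 80%.

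**2. Size of the overstatement.** With p_c the completer rate, the all-treated rate is (1 − d)·p_c + d·q. The per-protocol rate therefore exceeds it by d·(p_c − q). At p_c = 75% and d = 10%:
- q = 0: 0.10 × 0.75 = 7.5 points
- q = 25%: 0.10 × 0.50 = 5.0 points
- q = 75%: 0 points

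**3. Effect on the responder test, 30 evaluable subjects.** Fix the true all-treated rate at 50%. The completer rate is then (0.5 − d·q)/(1 − d), and the chance of passing is P(X ≥ 21) at that rate.

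| Withdrawn (assumed) | q = 0 | q = 25% | q = 50% (equal) |
|---|---|---|---|
| 5% | completer rate 52.6%; 4.1% | 51.3%; 3.0% | 50%; 2.1% |
| 10% | 55.6%; 7.8% | 52.8%; 4.2% | 50%; 2.1% |

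**4. Larger groups.** More subjects do not remove the bias. For an assumed 70 evaluable subjects in Group A the threshold is 44/70 (upper tail 2.1%). With d = 10% and q = 0 the chance of passing is 13.3%.

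**5. When it changes the result.** Count each withdrawn subject as a failure:
- 21/30: one added failure gives 21/31, p = 0.071, so significance is lost.
- 22/30: one is tolerated (22/31, p = 0.029).
- 23/30: three are tolerated (23/33, p = 0.035).
- 25/30: seven are tolerated (25/37, p = 0.047); an eighth is not (25/38, p = 0.073).

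The prior study cited in section 19.3 had 53.8% + 30.8% = 84.6% good or excellent, and 0.846 × 30 = 25.4, so the last line is close to that rate.

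**6. Group B.** The derived threshold mean is t(0.975, 33) × 2/√34 = 2.035 × 0.343 = 0.70. Adding five subjects with zero change gives a mean of 34 × 0.698/39 = 0.61, an SD of 1.88 and p = 0.0502. The p-value hardly moves because the added zeros shrink the SD from 2.00 to 1.88. That is an artefact of single imputation, and p still crosses 0.05.

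**The case against.** **The rates are assumed, and some loss is unrelated to response.** This stands. A positive pregnancy test leads to discontinuation (section 10.2) and says nothing about response. Subjects who only stop treatment early move into follow-up (section 6) and are not withdrawn. Hence the conditional form and the zero-bias column.

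**The promised SAP may add the analysis.** It may. The claim covers the supplied text only, and section 19.4 states a population rule that would still need to be aligned with such a SAP.

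**The plan is open about evaluable subjects.** Largely true: section 19.3 gives its power for evaluable subjects, so nothing needs adding there.

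**The status of the responder test is unsettled.** This stands. Sections 17.1 and 19.4 point to a mean or a paired t-test for pigment. The error rates above apply to the responder test of sections 17.3, 19.2 and 19.3 and not to a mean test. That conflict must be reconciled separately; the per-protocol restriction applies whichever test is kept.

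**A reader might infer that the error rate is badly out of control.** With 15–20% withdrawal and no response at all among the withdrawn, the same formula gives 14.5–25.8%. The documents do not support either assumption, so this is an extreme case and not the expected size.

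**Conclusion.** The point holds as a conditional one. The supplied plan tests effectiveness only in subjects who reach the final evaluation. In this uncontrolled design the Group A responder rate is overstated by d·(p_c − q) whenever withdrawn subjects respond less often. For the 30-evaluable case at 5–10% assumed withdrawal, the chance of passing at a true 50% rises from 2.1% to 3.0–4.2% (q = 25%) or 4.1–7.8% (q = 0), and by more in a larger group. It would decide the outcome only for results near the threshold.

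Two stronger readings are not supported. A reader might infer that the reported rate will be inflated; the documents do not show that loss will be selective. A reader might also infer that withdrawals would go unseen; the pre-lock deviation review and the safety counts could reveal their number. What is missing is a planned analysis of their effect. This is a cheap improvement; confidence is medium.

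**What to change.** In section 19.4, keep the per-protocol analysis and add beside it a pre-specified effectiveness analysis of all treated subjects in each group, including those later replaced.

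- **Group A responder rate.** Count subjects without an evaluable 12-week photograph as non-responders. Add a second version that uses the last post-treatment photograph already taken, at Treatment Visits 2–4 or at follow-up. The baseline photograph does not count.
- **Mean PCS and FWS change.** Use the same last photograph, or no improvement where there is none. Label this a sensitivity estimate and note that single imputation understates the variance.
- **Before imputing PCS.** Reconcile section 9.1 (0–4, with 0 as no improvement) with section 19.2 and Appendix A (1–5, with 1 as 0–24%). The imputed value depends on it.
- **Before defining a missing 12-week score.** Reconcile the ±2-week window (synopsis overview, section 10.3) with the ±4-week window (synopsis visit outline, Table 1).
- **Section 19.1.** State that major deviations are classified before evaluator scores are seen.

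The cost is plan wording and the scoring of existing photographs; no extra enrolment is required. The all-treated rate may be lower, and counting missing as failure is conservative if those subjects would have responded. The added test also has less power. With 30 completers at 75% response, power falls from 80% to 67% with one added failure (22/31 needed) and to 51% with three (23/33 needed). The last-photograph version limits this only for subjects who have such a photograph.
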